8.3 Efficacy assessments

Efficacy will not be measured in this study.

8.4 Safety assessments

The Sponsor may request additional information on specific adverse events or laboratory events of interest and may make requests to perform additional diagnostic tests to further assess the safety profile of sacubitril/valsartan. Such information may include diagnostic procedure reports, discharge summaries, autopsy reports, and other relevant information that may help in assessing the reported adverse event. All additional information will be de-identified prior to collection by Novartis or its agents.

In addition to AE/SAEs, the following safety-related evaluations will be done:

- Physical examinations (data recorded only in source)
- Vital signs
- Height, weight
- Laboratory evaluations

Pregnancy test

Safety assessments are specified below with Section 1.3 Schedule of Activities detailing when each assessment is to be performed.

For details on AE collection and reporting, refer to Section 8.6.

As per Section 4.5, during a public health emergency as declared by local or regional authorities i.e. pandemic, epidemic or natural disaster, that limits or prevents on-site study visits, regular phone or virtual calls can occur (every 3 months or more frequently if needed) for safety monitoring and discussion of the participant's health status until it is safe for the participant to visit the site again.

8.4.1 Physical examinations

A complete physical examination will include the examination of general appearance, skin, neck (including thyroid), eyes, ears, nose, throat, lungs, heart, abdomen, back, lymph nodes, extremities, vascular, and neurological. If indicated based on medical history and/or symptoms, rectal, external genitalia, breast, and pelvic exams will be performed.

Information for all physical examinations must be included in the source documentation at the study site. Clinically relevant findings that are present prior to signing informed consent must be recorded on the appropriate eCRF that captures medical history. Significant findings made after signing informed consent which meet the definition of an Adverse Event must be recorded as an adverse event.

8.4.2 Vital signs

Vital signs include blood pressure (BP) and pulse measurements and are assessed when a physical examination is performed. After the participant has been sitting for approximately 5 minutes, with back supported and both feet placed on the floor, systolic and diastolic blood pressure will be measured using an automated validated device, e.g. OMRON, or a standard sphygmomanometer with an appropriately sized cuff on the non-dominant arm. Supine BP instead of sitting BP will be measured in participants who are infants or who cannot sit comfortably. Clinically notable vital signs are defined in Appendix 3.

8.4.3 Height and weight

Height in centimeters (cm). It is recommended to measure standing height using a stadiometer without shoes.

Body weight (to the nearest 0.1 kilogram (kg) in indoor clothing, but without shoes) will be measured at every site visit. Body weight during hospitalization is to be recorded only if available as per standard of care.

8.4.4 Clinical safety laboratory tests

Laboratory assessments will be analyzed locally during the study. It is the responsibility of the Investigator to review all laboratory results and make an assessment of whether an abnormal or notable value is clinically significant, whether additional evaluations should be performed as

judged appropriate, and whether the patient may continue in the trial. Sample collection should be conducted according to the standards and requirements of the local laboratory.

Serum sodium, potassium, creatinine, and eGFR (modified Schwartz formula) will be evaluated locally at visits defined in Table 1-2, and recorded in the eCRF. Additional laboratory evaluation including hematology and urinalysis may be performed optionally by Investigator's clinical judgement at any visits. There is no local assessment at Visit Day1, but the results of central laboratory at the End of Study visit (Visit 599) in PANORAMA-HF OLE study should be reviewed by the Investigator soon after the results are obtained.

Clinically notable laboratory findings are defined in Appendix 3 Table 10-1. These findings must be commented on by the Investigator in the source documents and additional laboratory evaluations may be required, as judged appropriate by the Investigator.

If the laboratory abnormality induces clinical signs or symptoms, or requires therapeutic intervention, and satisfies the criteria defined in Section 8.6 Safety reporting, then the diagnosis or medical condition must be entered on the AEs page of the participant's eCRF and any treatment necessary should be documented. If the laboratory abnormality is the primary reason for an unforeseen hospitalization or otherwise fulfills the seriousness category of an AE, then the procedure for rapid notification of SAEs must be followed.

Likewise, if the laboratory abnormality leads to discontinuation of the study drug, the participant must be followed until the abnormality resolves or until it is judged to be permanent. This investigation may include continued monitoring by repeat laboratory testing or by performing additional laboratory tests as deemed necessary by the Investigator or the Sponsor's medical monitor.

For child bearing potential females only, serum pregnancy testing will be performed at the End of Study visit (Visit EOS). Please see details in Section 8.4.5.

A table, which provides the maximum, allowable blood-draw volumes by weight, can be found in Appendix 10.

Plasma potassium may be used instead of serum potassium in this study. Serum potassium thresholds in the study protocol, including those values cited in Appendix 3 and Appendix 9 can be converted to plasma potassium thresholds for the study by subtracting 0.4 mmol/L from the serum potassium threshold.

As per Section 4.5, during a public health emergency as declared by local or regional authorities' i.e. pandemic, epidemic or natural disaster, that limits or prevents on-site study visits, if participants cannot visit the site for protocol-specified safety lab assessments, an alternative lab (local) collection site may be used.

8.4.5 Pregnancy testing

All child-bearing potential female participants who are not surgically sterile will have pregnancy testing. Additional pregnancy testing might be performed if requested by local requirements.

Childbearing potential females (CHBP) are defined as all female participants ≥ 11 years of age and all female participants who are <11 years of age if they are menstruating. Pre-menarchal girls <11 years of age should notify the study site if they start menstruating after the study has started so pregnancy testing can be initiated. Urine pregnancy test is analyzed locally and done at all in-person scheduled/unscheduled visits (except for End of Study visit: Visit EOS) on all CHBP female participants. There is no assessment at Day1, but the result of central laboratory (serum test) at the End of Study visit (Visit 599) in PANORAMA-HF OLE study should be reviewed by the Investigator soon after the result is obtained. A positive urine pregnancy test should be confirmed with a serum pregnancy test. Participants with a positive serum pregnancy at any time in the study must be discontinued immediately from the study and should be seen at the site for Visit EOS. Serum pregnancy testing will be performed at Visit EOS.

For child-bearing potential females, a urine pregnancy test will also be performed at monthly intervals between study visits, during the study. The between-study-visit monthly urine pregnancy test can be performed either via: 1) monthly study site visits for urine pregnancy tests, or 2) providing the participant with urinary pregnancy tests for home monthly tests.

If monthly home urine pregnancy tests are utilized, child-bearing potential female participants will be given a urine pregnancy test kit for each month between study visits and will be instructed to perform a urine pregnancy test at home, once per month (approximately every 30 days). Participants will be given a Pregnancy Test Diary in which they are to record the date and the results of their pregnancy tests that are done at home, each time they run the test. Study Site personnel will contact the participant on a monthly basis to check that the participant has completed the urine pregnancy test and has recorded the result in the Pregnancy Test Diary. The Study Site personnel may also ask for the result of the pregnancy test. The contact by the Study Site personnel and the result of the pregnancy test will be documented in the source documentation for the participant. The Pregnancy Test Diary will be part of the source documentation for the participant. If the pregnancy test positive. is participant/parents/guardian must contact the Investigator immediately. The aforementioned pregnancy testing (i.e. done at home or at the study site) will be maintained during treatment and until the end of relevant systemic exposure.

All menarchal girls and their parents/caregivers should be informed about the potential risks of pregnancy and the need to prevent pregnancy during the study. It is important to be sensitive in introducing this issue, as understanding and comprehension of puberty, sexual activity, pregnancy and contraception is influenced by age; as well as, factors such as precocity, socioeducational economic and familial background. These discussions are therefore best performed by Investigators familiar with the pediatric participant and her family and should be guided by requirements of the local regulatory authorities. These discussions should take into account the socio-economic, cultural factors and religious beliefs of the adolescent participant and her family. The Investigator should also discuss the management of the pregnancy test results with the participant and her parents/caregivers. The privacy of the participant should be considered in accordance with the local law and ethics.

Any participant with a positive pregnancy test must discontinue study drug immediately, should be discontinued from the study, and should be seen at the site for Visit EOS.

Medical documentation of oophorectomy, hysterectomy, or tubal ligation must be retained as source documents. Subsequent hormone level assessment to confirm the female is not of child-bearing potential must also be available as source documentation in the following cases:

- 1. Surgical bilateral oophorectomy without a hysterectomy
- 2. Reported 12 months of natural (spontaneous) amenorrhea with an appropriate clinical profile.

In the absence of the above medical documentation, Follicle Stimulating Hormone (FSH) testing is required of any female participant regardless of reported reproductive/menopausal status at screening/baseline.

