- 1. Patients who permanently discontinued the study drug treatment during PANORAMA-HF OLE study cannot be enrolled in this study (Section 5.2), however, patients who temporally discontinued the study drug for any reason at the End of Study visit (Visit 599) in PANORAMA-HF OLE study may be enrolled in this study. In this case, the assessments specified for Visit Day1 should be performed at the visit when the study treatment starts. They will have to discontinue the study unless the study treatment starts within 3 months from Visit Day1, and will be considered an early study termination (Section 5.3).
- 2. End of Study (EOS) visit will be completed when marketed product of sacubitril/valsartan pediatric formulation becomes commercially available in Japan, the study treatment is permanently discontinued based on the Investigator's judgement, or participant prematurely withdraws from the study, whichever occurs first.
- 3. Signed informed consent as well as assent at an appropriate age must be obtained prior to participation in the study. Patient Assent document is captured as a source document and is not stored in the clinical database.
- 4. If the trial is extended 1 year or over, height at Visit M12 should be recorded in the electronic Case Report Form (eCRF)
- 5. The data measured at the End of Study visit (Visit 599) in PANORAMA-HF OLE study will be utilized as the data at Visit Day1 for this study.

6. Serum sodium, potassium, creatinine, and estimated Glomerular Filtration Rate (eGFR, modified Schwartz formula) will be measured locally, and recored in the eCRF. Additional laboratory evaluation including hematology and urinalysis may be performed optionally by Investigator's clinical judgement at any visits. There is no local assessment at Visit Day1, but the results of central laboratory at the End of Study visit (Visit 599) in PANORAMA-HF OLE study should be reviewed by the Investigator soon after the results are obtained.

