7. For child-bearing potential females (CHBP) only. Urine pregnancy test is analyzed locally and done at Visit M6 and unscheduled visits on all female participants ≥11 years of age and all female participants who are <11 years of age if they are menstruating. There is no assessment at Visit Day1, but the result of central laboratory (serum test) at the End of Study visit (Visit 599) in PANORAMA-HF OLE study should be reviewed by the Investigator soon after the result is obtained. Additionally, for all CHBP, a urine pregnancy test will be performed at monthly intervals during the study. The monthly urine pregnancy test can be performed either via: 1) monthly study site visits for urine pregnancy tests, or 2) providing the participant with urinary pregnancy tests for home monthly tests. See Section 8.4.5 for additional details. A serum pregnancy test is performed and analyzed locally at Visit EOS.

2 Introduction

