the participant can be up-titrated to the next higher dose level using unscheduled visits in an attempt to bring back the participant gradually to the target study drug dose level. The Investigator may select the next dose level for down- or up-titration according to his or her judgment (Table 4-1). For up-titration of the study drug, participants have to meet all criteria in Table 6-2 before administering the higher dose level.

Table 6-2 Safety monitoring criteria for adjustment of study-drug dose level

Parameter	Description
Potassium level	Serum K ≤ 5.4 mmol/L (mEq/L) or plasma K ≤ 5.0 mmol/L (mEq/L)
Kidney function	eGFR (calculated using the modified Schwartz formula) ≥ 30% mean GFR for age (Appendix 5, Table 10-4)
Kidney function	eGFR reduction < 35% compared to Visit Day1.
Blood pressure	Systolic blood pressure (SBP) > than the calculated 5 th percentile SBP for age as described in Appendix 7
AEs or conditions	No conditions that preclude continuation according to Investigator's judgment, including hypotension.

All changes should be recorded on the DAR eCRF.

Study drug restart after temporary treatment interruption

Participants who have temporarily discontinued study drug should be restarted as soon as possible as deemed appropriate by the Investigator. The Investigator should restart the participant on the study drug at the most appropriate dose level (Table 4-1) as per the Investigator's clinical judgment. If the participant does not tolerate the newly restarted studydrug dose level, they may be down-titrated again (if appropriate) or the study medication may be temporarily discontinued again.

Participants restarted on the study drug will retain their original study identification numbers.

Investigators may discontinue a participant's study drug due to serious or intolerable AEs suspected to be causally related to study drug. If study drug is discontinued for any reason, this must be recorded on the DAR eCRFs. In addition, participants who permanently discontinued study drug should be scheduled for the discontinuation study Visit EOS. Note that after a consecutive 3-month interruption of study treatment, participant should be discontinued from the study and should be seen at the site for Visit EOS).

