Sacubitril/valsartan treatment will start at Visit Day1, which is the same day as the End of Study visit (Visit 599) of PANORAMA-HF OLE study. The data of some assessments (such as vital sign, height, and weight) at the End of Study visit (Visit 599) in PANORAMA-HF OLE study will be utilized as the data at Visit Day1 for this study.

A telephone visit (Visit M3) and an on-site visit (Visit M6) will occur 3 months and 6 months after Visit Day1, respectively. The visits as same Visit M3 and Visit M6 will then be repeated every 3 months until the end of the study. When the pediatric formulation of sacubitril/valsartan becomes available in Japan, or this study is terminated by Novartis, any participants should return to the study site as soon as possible for End of Study (EOS) visit (Visit EOS) regardless of subsequent scheduled visit, and all of the assessments listed for Visit EOS will be performed.

Participants should take their scheduled dose of sacubitril/valsartan in the morning of their study visits. Participants are not required to fast overnight on the day prior to or the day of the study visit.

Participants, who discontinue sacubitril/valsartan for 3 consecutive months, will be discontinued from the study and are to attend Visit EOS.

Participants should be seen for all visits/assessments as outlined in the assessment schedule or as close to the designated day/time as possible. If one visit is postponed or brought forward, it should not result in the next visit being postponed or brought forward. The next visit, if at all possible, should adhere to the original schedule in relation to Visit Day1. Missed or rescheduled visits should not lead to automatic discontinuation. Specific circumstances surrounding missed or rescheduled visits must be discussed with the study monitor. Participants who prematurely discontinue the study treatment, or prematurely withdraws from the study for any reason should be scheduled for a final visit as soon as possible, at which time all of the assessments listed for the final visit (Visit EOS) will be performed. At this final visit, all dispensed investigational

product should be reconciled, and the adverse event and concomitant medications recorded on the eCRF.

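### Pregnancy is an exclusion and drug is dispensed at Visit Day1, but no pregnancy result has to be known, or negative, before that first dispensing

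*Protocol*

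**What the plan says.** Pregnant or nursing patients are ineligible (Protocol Section 5.2, exclusion 7). Section 8.1 has the entry criteria checked at Visit Day1. Section 8 places the start of treatment at the same visit: "Sacubitril/valsartan treatment will start at Visit Day1, which is the same day as the End of Study visit (Visit 599") of the parent open-label extension. Table 1-2 marks drug dispensing at Day1. Its pregnancy-test row has entries for M6, unscheduled visits and EOS, but none for Day1.

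Section 8.4.5 gives the general rule that a local urine test is "done at all in-person scheduled/unscheduled visits (except for End of Study visit: Visit EOS) on all CHBP female participants". It then exempts Day1: "There is no assessment at Day1, but the result of central laboratory (serum test") taken at Visit 599 is to be reviewed shortly after it becomes available. Footnote 7 of Table 1-2 says the same.

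Other safeguards are in place. Exclusion 8 requires highly effective contraception. Footnote 7 adds, "Additionally, for all CHBP, a urine pregnancy test will be performed at monthly intervals during the study". Section 8.4.5 states, "Any participant with a positive pregnancy test must discontinue study drug immediately".

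**The concern.** Eligibility on pregnancy is decided, and drug handed over, at a visit where this study does no pregnancy test. The only result these documents name for that day comes from a central laboratory, and the plan expects the investigator to read it when it comes back. A site could follow the protocol exactly and dispense before knowing the result.

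The stake is fetal exposure. The benefit/risk section tells females of child-bearing potential that the risks to a fetus are unknown, and SAP Section 2.7.1.1 lists embryo-fetal toxicity among the events of special interest. This is a participant-safety point. It does not affect the adverse event summaries, and pregnancy tests are kept in source documents only.

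**Working it through.** The plan states no figure to reproduce, so the check is mainly one of order and coverage.

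**Order of events at Day1**

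1. Consent is signed and the criteria, including exclusion 7, are checked (Sections 8 and 8.1, Table 1-2).
2. Drug is dispensed and treatment starts (Sections 4.1 and 8, Table 1-2).
3. The Visit 599 central serum result is reviewed after it arrives (footnote 7, Section 8.4.5).

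No sentence in the protocol or SAP moves step 3 ahead of step 2. Exclusion 7 bars a patient known to be pregnant, but it names no test and no required result.

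**Pregnancy tests by in-person visit (Table 1-2)**

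| Visit | Test in this study |
|---|---|
| Day1 | none; same-day Visit 599 central serum |
| M6 | local urine |
| Unscheduled | local urine (not marked optional) |
| EOS | local serum |

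Day1 is the only in-person visit without this study's own test.

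**What the other safeguards do**

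- Stopping drug on a positive test acts only once a positive result exists.
- Monthly urine tests run about every 30 days during the study, so the first may come well after Day1.
- Contraception lowers the chance of pregnancy but does not verify status.

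**Late starters**

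Footnote 1 allows treatment to start up to 3 months after Day1, and then "the assessments specified for Visit Day1 should be performed at the visit when the study treatment starts". M3 is a telephone visit, and M6 is day 183 (SAP Section 2.1.1), beyond the 3-month limit. The start visit is therefore ordinarily an unscheduled in-person visit, where a urine test is already required. What is missing there is only the link between the result and dispensing.

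**Size**

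- Participants affected: at most 8 enrol. The number of child-bearing potential is not given, so the range is 0 to 8.
- Doses between Day1 and the central result: 2 per day (Table 4-1) × turnaround in days. Turnaround is not given. At an assumed 1 to 7 days this is 2 × 1 = 2 to 2 × 7 = 14 doses.
- Most entrants are already on drug, and Sections 1.3 and 8 tell participants to take the morning dose on visit days. For them these doses are continued exposure, and a dose will often precede the visit. The figure is new exposure only for a patient temporarily off drug who restarts on Day1.
- Extra kits: 1 per participant of child-bearing potential, so 0 to 8.
- Expected false positives with 8 tests, at an assumed rate of 0.5% to 2% per test: 8 × 0.005 = 0.04 to 8 × 0.02 = 0.16 in the whole study.

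**The case against.** The strongest reply is that this is a deliberate rollover design. Pregnancy is tested that day, by a serum test, and repeating it locally could be called duplication. Chemistry is handled the same way: no local sample at Day1, with central Visit 599 results reviewed when they arrive. Sections 4.3 and 8.4.7 describe the design and safety assessments as similar to the parent study's, which points towards recent testing before Day1. The parent protocol is not available, so a local urine test at or near Visit 599 may already be required. Section 10.1.8 also lets sites add assessments needed for safety. Most entrants are continuing drug, so a Day1 gate would not prevent their first exposure.

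All of this bears on size, and it stands. It does not supply the missing condition: a same-day sample whose result comes later cannot confirm eligibility at the visit, and discretion to add a test is not a requirement to have its result.

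A reader might infer two stronger points that the documents do not support:

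- **An inconsistency with the up-titration rule.** Section 6.4.1 says "participants have to meet all criteria in Table 6-2 before administering the higher dose level", so the protocol can write a condition before dosing. But that rule governs dose increases, its criteria do not include pregnancy, and Day1 is usually continuation. Day1 is not gated on potassium or eGFR either.
- **A late starter relying on an old result.** The Day1 exemption rests on the same-day Visit 599 serum test, which a later start visit does not have. The rule for in-person visits then applies, and footnote 7 repeats it: "Urine pregnancy test is analyzed locally and done at Visit M6 and unscheduled visits on all female participants". Whether footnote 1 carries the exemption forward could be clearer, but the natural reading requires a urine test at the start visit.

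**Conclusion.** The point holds as a minor safety gap. Exclusion 7 is applied and drug dispensed at Day1, this study does no pregnancy test that day, and no text requires a negative result before first dispensing.

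The practical effect is small: 0 to 8 participants, with contraception, monthly testing and an immediate stop rule in place. For those continuing drug, a Day1 test would shorten further exposure by the central turnaround. It would prevent re-exposure only in patients temporarily off drug who restart on Day1. It should not be read as 2 to 14 doses of new exposure in every entrant.

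The conclusion rests on the two documents alone. The turnaround and false-positive rates are assumptions, and the number of child-bearing potential and the parent study's local testing are unknown. If the parent study already requires a negative local urine test at or near Visit 599, stating that here would largely close the gap. If all participants have already started, the change serves only as clarification.

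**What to change.** Put S (Urine) in the Day1 cell of the pregnancy row in Table 1-2. In footnote 7 and Section 8.4.5, replace the Day1 exemption with wording to this effect:

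> A local urine pregnancy test is done for all females of child-bearing potential at Visit Day1, or at the treatment-start visit if later. Study drug is dispensed only after a negative result. A positive urine test is confirmed by a serum test, and drug is withheld meanwhile. The Visit 599 central serum result is reviewed as confirmation.

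This also removes any doubt about late starters. The cost is at most 8 extra urine kits of a type already used at M6 and unscheduled visits, with no added visit or blood draw. The downside is a short delay to heart failure treatment after a false-positive urine test, which should be rare. A negative result causes no delay beyond the visit. Cheap improvement, minor safety priority.
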